## **6.1. Subject Assignment to Treatment and Masking**

Each subject complying with the inclusion/exclusion criteria who is willing to participate in the study, and signs the informed consent, will be enrolled. At baseline subjects will be randomized to use the system for 30 minutes either one (1) time per week or three (3) times per week for a total of 12 weeks. All subjects will independently complete stimulation treatment sessions; no blinding will occur

# **7. Methods and Procedures**

## **7.1. Informed Consent**

Written Informed Consent will be obtained from each subject prior to any study procedures being performed. All potential subjects will be properly informed as to the purpose of the study and the potential risks and benefits known or that can be reasonably predicted or expected. The Investigator will retain the original copy of the Informed Consent Form signed by the subject; a duplicate will be provided to the subject. Only the consent form approved by the ethics committee will be used.

## **7.2. Visit Schedule**

	Study Visit	Tele-visit
Screening 1	Visit 0	
Screening 2/ Baseline	Visit 1	
Week 1	Visit 2	optional
Week 2		X (Weekly Phone Call)
Week 3		X (Weekly Phone Call)
Week 4	Visit 3	optional
Week 5		X (Weekly Phone Call)
Week 6		X (Weekly Phone Call)
Week 7		X (Weekly Phone Call)
Week 8	Visit 4	optional
Week 9		X (Weekly Phone Call)
Week 10		X (Weekly Phone Call)
Week 11		X (Weekly Phone Call)
Week 12	Visit 5	

### **7.3. Pre-Screening**

Potential study candidates will be initially pre-screened by the investigator prior to screening and enrollment according to the Inclusion and Exclusion criteria.

### **7.4. Visit 0 - Screening 1 (Informed Consent and Diary Distribution)**

This visit involves the review and signing of the Informed Consent, eligibility criteria review, and distribution of a 3-day Bladder Diary.

Step	Action
1.	Subjects will be informed of the study and review the informed consent.
2.	Subjects will be given a 3-day Bladder Diary to take home and complete within 3 days leading up to their scheduled Visit 1.
Note	Only subject that sign the informed consent will be given the 3-day Bladder Diary.

### **7.5. Visit 1 - Screening 2 (EMG evaluation)**

This procedure will evaluate if EMG signals can be recorded during stimulation of the tibial nerve with the wearable bladder modulation system.

Step	Action
1.	Screening evaluations will be collected including (using a 3-day Bladder Diary): 

1. Number of daytime voids

2. Number of urge events

3. Number of nighttime voids

4. Number of urge incontinence events

Note	Only subjects that meet the inclusion/exclusion criteria with regard to the Bladder Diary will proceed to EMG testing.
2.	Only delegated, qualified, site personnel will instruct the subject on how to place the Test Article on the foot and ankle area.
3.	Once the Test Article is placed, site personnel will use the Test Article to stimulate the tibial nerve, evaluate EMG signals and instruct the subject how to use the Test Article.
4.	The subject will be asked to rate various sensations experienced during the stimulation therapy.
5.	Subject will be enrolled in the study and given a subject ID.
Note	Only subjects that have a detectable EMG and find the stimulation sensation tolerable will be eligible for enrollment.

## 7.6. Visit 1- Baseline Evaluations

These evaluation procedures outline the baseline evaluation that will take place before a subject begins stimulation therapy. These procedures can also be done during the Screening 2 / Baseline visit.

Step	Action
1.	The inclusion and exclusion criteria will be confirmed as being met
2.	Demographic information will be collected.
3.	OAB questionnaires will be completed including: 1. OAB-q 2. IIQ-7 (only for those with incontinence) 3. I-QoL 4. and OHQ
4.	Subjects will be randomized 1:1 to perform 30-minute stimulation sessions once per week or three times per week for the 12-week treatment period.

## 7.7. Visit 1- System fitting and training

This procedure outlines the training that will take place before the subject begins stimulation.

Step	Action
1.	The subject will be fitted for the Test Article.
2.	The subject be given instruction by site personnel as to how to use the Test Article.
3.	Once the Test Article is placed, the subject will use the controller to start the stimulator to activate the tibial nerve (trial session should not exceed 15 minutes).
4.	The subject will be asked questions regarding the feeling of Test Article during use and the ease of use of the Test Article.
5.	Subjects will be given a new 3-day Bladder Diary to complete in the days leading up to the next scheduled study visit.

## 7.8. Visit 2 - Week 1 ± 2 days

This visit will be scheduled after 1 week of therapy for evaluations. This visit may be performed remotely via ePRO.

Step	Action
1.	Subjects will be queried for AE/SAE or concomitant medication changes.
2.	The 3-day Bladder Diary dispensed at Visit 1 will be collected and reviewed.
3.	Applicable visit forms and questionnaires will be completed.
4.	The subject will be asked questions regarding the feeling of the therapy and ease of use of the Test Article.
6.	Subjects will be given a new 3-day Bladder Diary to complete in the days leading up to the next scheduled study visit.

## 7.9. Visit 3 - Week 4 ± 4 days

This visit will be scheduled after 4 weeks of therapy for evaluations. This visit may be performed remotely via ePRO.

Step	Action
1.	Subjects will be queried for AE/SAE or concomitant medication changes.
2.	The 3-day Bladder Diary dispensed at Visit 2 will be collected and reviewed.
3.	Applicable visit forms and questionnaires will be completed: 1. OAB-q 2. IIQ-7 3. I-QoL 4. PGIC
4.	The subject will be asked questions regarding the feeling of the therapy and ease of use of the Test Article.
5.	Subjects will be given a new 3-day Bladder Diary to complete in the days leading up to the next scheduled study visit.

#### **7.10. Visit 4 - Week 8 ± 4 days**

This visit will be scheduled after 8 weeks of therapy for evaluations. This visit may be performed remotely via ePRO.

Step	Action
1.	Subjects will be queried for AE/SAE or concomitant medication changes.
2.	The 3-day Bladder Diary dispensed at Visit 3 will be collected and reviewed.
3.	Applicable visit forms and questionnaires will be completed
4.	Subjects will be given a new 3-day Bladder Diary to complete in the days leading up to the next scheduled study visit.

#### **7.11. Visit 5 – Week 12 ± 4 days**

This visit will be scheduled after 12 weeks of stimulation for final evaluations.

Step	Action
1.	Subjects will be queried for AE/SAE or changes to concomitant medications.
2.	The 3-day Bladder Diary dispensed at Visit 4 will be collected and reviewed.
3.	Applicable visit forms and questionnaires will be completed, including the Study Exit Form.
4.	The subject will be asked questions regarding the feeling of the therapy and ease of use of the Test Article.
5.	Subjects will either exit from the study or be given the option to enroll in the long-term follow-up study, if eligible.

## 7.12. Visit Schedule for Lead-in Phase

## 8. Long-Term Follow-Up Phase

### 8.1. Subject Selection

Selection Criteria	
Inclusion Criteria: To be eligible for entry into the long-term follow-up portion of the study, subjects must satisfy all the following inclusion criteria:
 

1. Successful completion of the lead-in portion of the FREEOAB study

2. A rating of 5 or greater on the PGIC questionnaire at Visit 5

3. A minimum compliance of 90% with diary and questionnaire completion

4. A minimum compliance of 80% with stimulation sessions during the lead-in portion of the FREEOAB study.

 
Exclusion Criteria: Subjects will be excluded from participation if the following exclusion criteria are met:
 

1. Any change in health status that might affect the subject's ability to comply with the visit schedule, assessments, and/or stimulation session completion.

---------------------------	--

### 8.2. Informed Consent

Written Informed Consent will be obtained from each subject before recruitment into the long-term follow-up portion of the FREEOAB trial. All potential subjects will be properly informed as to the purpose and the potential risks and benefits known or that can be reasonably predicted or expected. The Investigator will retain the original copy of the Informed Consent Form signed by the subject; a duplicate will be provided to the subject. Only the consent form approved by the ethics committee will be used.

### 8.3. Visit Schedule

	Study Visit (in-clinic)	Remote/Tele-visit
Enrollment	Visit 6	
Month 6		Visit 7
Month 9		Visit 8
Month 12	Visit 9	Optional
Month 18		Visit 10
Month 24	Visit 11	

### 8.4. Visit 6 - Enrollment

This procedure will occur at the completion of Visit 5/Week 12 of the lead-in portion of the FREEOAB study. Eligible subjects will sign a new Informed Consent Form. (Visit 5 and 6 may occur on the same day)

Step	Action
1.	Eligible subjects that elect to enroll in the long-term follow up study will sign a new informed consent form.
2.	Subjects will be given detailed instructions to begin an augmented treatment schedule, based on original treatment group assignment in the lead-in portion of the study. 
 
Subjects will be instructed to slowly taper down their treatment frequency stepwise from three treatment sessions per week, to two per week, to one per week, and finally one session every other week.
 
Subjects that were assigned to one treatment session per week in the lead-in portion will move directly to twice monthly treatment sessions.
 

3.	Subjects will be given a new 3-day Bladder Diary to complete within 3 days leading up to their next scheduled visit.

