## 2. Protocol Summary

Title	A prospective efficacy study comparing frequency of use and efficacy of a surgery-free wearable personalized bladder modulation system with objective confirmation of nerve activation for use in the home by subjects with Overactive Bladder syndrome.
Test Article	Avation Medical's surgery-free wearable and personalized bladder modulation system that provides objective confirmation of nerve activation, can be used in a home environment, and is controlled with a tablet-based application
Protocol Number	AMHOAB2001
Objectives	
 
• To compare the effectiveness of 1 treatment session per week to 3 treatment sessions per week on OAB symptoms using the Test Article.
 
• To evaluate the overall effectiveness.
 
• To evaluate any side effects of the Test Article.
 
• To evaluate the tolerability, usability, and satisfaction of the Test Article.
 
• To evaluate the compliance of subjects using the Test Article.
 

Subject Population	Subjects diagnosed with OAB.
Population Size	80 completed subjects
Number of Centers	Up to 12 sites
Structure	Prospective open label study, 12-week treatment duration with an optional additional 21-month long-term follow-up period, for a total participation time of 24 months.
Method of Assignment	All subjects who meet the inclusion/exclusion criteria and sign the informed consent will be enrolled. Subjects will be randomized to once a week or three times a week of stimulation for a twelve-week period. Eligible subjects that elect to enroll in the long-term follow up study will sign a new informed consent and then be instructed to slowly taper down their treatment frequency stepwise from three treatment sessions per week, to two per week, to one per week, and finally one session every other week. The subjects that were assigned to one treatment session per week in the lead-in portion of the study will move directly to twice monthly treatment sessions. Subjects will then be instructed to perform treatments as needed or a minimum of twice per month.

Randomization	1:1, 1 treatment session per week: 3 treatment sessions per week

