#### 10.4. Controller

The Stimulator will be controlled using an application on a tablet. This tablet will be supplied by the Sponsor and will only be enabled as a controller for the stimulator.

The controller application will have screens which will allow both the physician and subject to easily interact with the stimulator. Data collected by the stimulator will be transmitted to a HIPAA-compliant cloud to allow the investigators and Sponsor to easily review the subject's usage of the system while completing their treatment sessions at home. This will also allow troubleshooting to take place without a visit to the office.

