### **13.2. Analysis of Efficacy and Sample Size**

Using data collected at each of Study Visits 2, 3, and 4, percent change from screening at each time point will be calculated for each patient with respect to frequency of OAB symptoms, including 3-day daily averages of daytime voids, urge events, nighttime voids, and urge incontinent events. The maximum percent improvement across the four symptoms will also be calculated at each time point as a composite endpoint. Percent improvement in daily average total voids relative to an upper normal limit of 8, will also be calculated, and will be bounded below at 0% for patients not achieving improvement and bounded above at 100% for patients achieving or surpassing the upper normal limit of 8. Longitudinal analyses will be performed using repeated measures models to assess and describe trends over time with respect to these endpoints. At individual time points, the one-sample T-test will be performed at significance level  $\alpha=0.05$  within each treatment group and for the pooled study groups to assess the mean percent improvements, with 95% confidence intervals for mean percent improvements also calculated. The percent change endpoints are not likely to have approximately normal distributions, but the sample size is considered sufficient such that mean values will be approximately normally distributed, justifying the use of the T-tests. If there is concern with the distributions, then the Wilcoxon signed rank test will be used as an alternative to the one-sample T-test.

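### The long-term treatment schedule differs between sections: Sections 2 and 5 end in as-needed use with a twice-monthly minimum, a step missing from the Visit 6 instructions, and no section gives the length of a taper step

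*Combined protocol and SAP*

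**What the plan says.** The Protocol Summary (Section 2, Method of Assignment) and Section 5 (Study Design) describe the long-term phase in the same way. The three-per-week group steps down to a session every two weeks, the once-weekly group goes straight to twice monthly, and then: "Subjects will then be instructed to perform treatments as needed or a minimum of twice per month".

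Section 8.4 (Visit 6 - Enrollment) is where sites instruct subjects. It opens with "Subjects will be given detailed instructions to begin an augmented treatment schedule", although what follows is a reduction. For the three-per-week group it says "Subjects will be instructed to slowly taper down their treatment frequency stepwise", with the last step written as "to one per week, and finally one session every other week". The once-weekly group "will move directly to twice monthly treatment sessions". Section 8.4 has no as-needed step. Sections 8.5 to 8.9 (Visits 7 to 11) contain no instruction on treatment frequency.

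The table in Section 8.11 has PGIC at every visit from Month 6 to Month 24, and its notes have a bladder diary collected at each of them. Section 10.4 says stimulator data are transmitted so that investigators and the sponsor are able "to easily review the subject's usage of the system while completing their treatment sessions at home". The efficacy analysis in Section 13.2 begins "Using data collected at each of Study Visits 2, 3, and 4" and names no long-term visit.

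**The concern.** Section 8.4 holds the only frequency instruction in Section 8, and after Visit 6 the next scheduled contact is Month 6. With up to 12 sites, one working from Section 8.4 and another working from Section 5 could in good faith tell subjects different things for up to 21 months.

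The difference affects what the long-term data mean. On a fixed low frequency, the Month 6 to 24 diaries and PGIC ratings describe how subjects fare at that frequency. With as-needed use, a subject whose symptoms return may treat more, so the dose is partly a consequence of the outcome. A stable average would then be compatible both with lasting benefit at low use and with benefit held up by extra sessions. Compliance, which Section 4 lists as an objective, also has no clear denominator in the long-term phase without one agreed schedule.

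**Working it through.** **1. Follow-up length.** Section 2 gives "12-week treatment duration with an optional additional 21-month long-term follow-up period, for a total participation time of 24 months". With 365.25 / 12 / 7 = 4.348 weeks per month, 12 / 4.348 = 2.76 months, and 2.76 + 21 = 23.76 months. This agrees with the stated 24.

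**2. The texts side by side.**

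| Element | Sections 2 and 5 | Section 8.4 |
|---|---|---|
| Three-per-week group | Step down to every other week | Same |
| Once-weekly group | Straight to twice monthly | Same |
| After that | As needed, with a twice-monthly minimum | Nothing stated |
| Upper limit on sessions | None stated | Not needed if the frequency is fixed |
| Length of each taper step | Not stated | Not stated |

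The taper agrees in all three places. The mismatch is the step that follows it.

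**3. Sessions over Months 6 to 24 (18 months).** I assume the taper is complete by Month 6, which the documents do not say. Sessions = rate per month × 18.

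| Use | Calculation | Sessions |
|---|---|---|
| Twice monthly (end point in the once-weekly group; also the minimum in Sections 2 and 5) | 2 × 18 | 36 |
| Every other week (end point in the three-per-week group) | 4.348 / 2 × 18 | about 39 |
| As needed, assumed 1 per week | 4.348 × 18 | about 78 |
| As needed, assumed 3 per week | 3 × 4.348 × 18 | about 235 |

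At the minimum, the two versions give 36 against 36 to 39 sessions, a ratio of 0.92 to 1. At the assumed rates, the ratios to every other week are 78 / 39 = 2.0 and 235 / 39 = 6.0. The rates of one and three per week are illustrations; the documents give no figure for as-needed use.

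**4. The taper assumption.** Month 6 counts from the start of treatment, so it falls 6 × 4.348 − 12 = 14.1 weeks after Week 12. If the reduction starts at once, two steps (two per week, then one per week) come before every other week. They are finished by Month 6 only if they average no more than 14.1 / 2 = about 7 weeks each. Because the step length is not stated, the intended frequency at Month 6 in the three-per-week group cannot be determined from any section.

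**The case against.** The strongest reply is that this is an omission and not a contradiction. The taper steps agree everywhere, Sections 2 and 5 place as-needed use after the taper, and Section 8.4 describes how to begin the schedule, so the texts can be read in sequence. The detailed instructions and the new consent form to which Section 8.4 refers are not available here and may carry the missing step. That sites would actually diverge is a possibility, not a documented fact. This stands as far as it goes, but the protocol should not depend on unseen material for its treatment schedule, and no later visit procedure repairs the gap.

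A reader might infer that the long-term phase has no defined dose. The documents do not support that: Sections 2 and 5 state a minimum, and it is close to the taper end point (2 against about 2.17 sessions per month). Reading the sentence as an alternative with no floor leaves its reference to a minimum without meaning, though the wording should be made plain.

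A reader might also infer that the long-term data are uninterpretable. That goes too far, because home use is transmitted and delivered dose can be described. Nor does the protocol claim durability at a fixed frequency: no objective in Section 4 names it, and no test in Section 13 depends on it. The phase is also optional, open label and restricted to subjects with a PGIC rating of 5 or more and at least 80% session compliance, so a strong durability claim would be limited in any case.

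What remains is that the instruction differs by section, and that Section 13 plans no analysis of use that would show which schedule was followed.

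**Conclusion.** The point holds as an inconsistency that should be corrected. The long-term instruction in Sections 2 and 5 has a minimum and no stated upper limit; the one in Section 8.4 ends at a fixed low frequency; none gives the length of a taper step. The resulting difference in exposure over Months 6 to 24 ranges from essentially none, if subjects stay at the minimum, to about two- to six-fold at an assumed one to three sessions per week. The larger figures rest wholly on that assumption and on the taper being complete by Month 6, so a several-fold difference is possible but not established.

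The consequence is limited to interpretation. If use was as needed, Month 6 to 24 results cannot be presented as durability at a fixed reduced frequency. The randomised 12-week comparison, the sample size and its power figures do not depend on this point. Section 17.1 says the study data will support a 510K clearance, so the limits of any long-term claim are worth settling in advance.

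**What to change.** - Reconcile Sections 2, 5 and 8.4 so that one instruction, chosen by the sponsor, appears in all three. It should state whether twice per month is a floor and how long each taper step lasts. Which schedule applies is for the sponsor to decide.
- Correct the word in Section 8.4 that describes the reduced schedule as augmented.
- Add to Section 13 a table of Month 6 to 24 diary and PGIC results beside the number of sessions delivered in a pre-specified window before each diary, using the usage data already transmitted under Section 10.4.
- If the as-needed text is kept, label these results as outcomes under self-selected use.

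The cost is a wording amendment, a memo to sites and one extra table from data already collected. The downside is a narrower long-term claim if as-needed use is kept.

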#### **8.5. Visit 7 - (Month 6 ± 14 days of stimulation)**

Visit 7 will occur after 6 months of treatment (including lead-in portion of the FREEOAB study). This visit may be conducted remotely, via ePRO.

Step	Action
1.	Subjects will be queried for AE/SAE or concomitant medication changes.
2.	The 3-day Bladder Diary dispensed at Visit 6 will be collected and reviewed.
3.	Applicable visit forms and questionnaires will be completed
4.	Subjects will be given a new 3-day Bladder Diary to complete within 3 days leading up to their next scheduled visit.

#### **8.6. Visit 8 – (Month 9 ± 14 days of stimulation)**

Visit 8 will occur after 9 months of treatment (including lead-in portion of the FREEOAB study) . This visit may be conducted remotely, via ePRO.

Step	Action
1.	Subjects will be queried for AE/SAE or concomitant medication changes.
2.	The 3-day Bladder Diary dispensed at Visit 7 will be collected and reviewed
3.	Applicable visit forms and questionnaires will be completed

4.	Subjects will be given a new 3-day Bladder Diary to complete within 3 days leading up to their next scheduled visit.
----	--

#### **8.7. Visit 9 – (Month 12 ± 14 days of stimulation)**

Visit 9 will occur after 12 months of treatment (including lead-in portion of the FREEOAB study). This visit may be conducted remotely via ePRO.

Step	Action
1.	Subjects will be queried for AE/SAE or concomitant medication changes.
2.	The 3-day Bladder Diary dispensed at Visit 8 will be collected and reviewed.
3.	Applicable visit forms and questionnaires will be completed.
4.	Subjects will be given a new 3-day Bladder Diary to complete within 3 days leading up to their next scheduled visit.

